1 STUDY RATIONALE/BACKGROUND

Alvimopan (Entereg) is an orally administered peripherally acting μ -opioid receptor antagonist that has been shown to decrease the duration of postoperative ileus.^{2,5,8,9} Multiple double-blinded, randomized, placebo-controlled trials, have shown Alvimopan to reduce both the time to gastrointestinal recovery and the time to hospital discharge following bowel resection. This benefit was achieved without compromising pain management.¹⁰ Alvimopan selectively and competitively inhibits the μ -opioid receptors in the GI tract, but is unable to cross the blood-brain barrier. This prevents Alvimopan from affecting the central nervous system pathway that controls analgesia, allowing it to decrease postoperative ileus time without compromising pain control.¹⁰ In addition to accelerated gastrointestinal recovery and reduced length of hospital stay, the use of Alvimopan also significantly decreased the number of adverse events (most notably nausea and vomiting), and decreased the need for postoperative nasogastric tube reinsertion. These improved clinical outcomes had further impact by leading to lower hospital costs and increased patient satisfaction.^{3,5,8,9} Alvimopan is FDA approved for patient use with the intent of accelerating upper and lower gastrointestinal recovery following bowel resections. To date, no studies have been conducted regarding the use of Alvimopan in patients undergoing ventral hernia repairs.

Conservative estimates suggest that the incidence of ventral incisional hernia after abdominal surgery via midline laparotomy is 10-20%.^{1,4,7} The occurrence of a ventral incisional hernia is associated with significant patient discomfort, disability and subsequent morbidity. These factors lead most patients suffering from a ventral incisional hernia to pursue elective repair. In 2005, there were greater than 348,000 ventral hernia repairs in the United States alone.¹⁴ If left unrepaired, these hernias can

increase in size causing pain, abdominal wall deformity, skin breakdown, intestinal obstruction and/or intestinal strangulation.⁴

One of the most common occurrences following ventral incisional hernia repair is post-operative ileus. Post-operative ileus is a source of patient discomfort and morbidity that ultimately delays discharge from the hospital and is frequently a source of patient readmission. Prolonged length of hospital stay due to post-operative ileus increases direct health care costs, as well as the indirect costs of a delay in returning to the workforce. The cause of prolonged ileus is multifactorial, but some of the main culprits include intra-operative bowel manipulation, the release of endogenous opioids, the administration of exogenous opioid analgesics during surgery and for post-operative pain control, inflammation, and fluid shifts.^{3,5,8} A study by Lowe et al showed that following ventral hernia repair, 27% of their study patients had a prolonged ileus, defined as lasting more than 7 days postoperatively.⁴ Likewise, the mean hospital stay for these patients was 12.5 days, due most frequently, to a delayed return of bowel function.⁴

Ventral incisional hernia repair is a common operation and post-operative ileus remains a frequent and costly post-operative occurrence for which we do not currently have an effective therapy. Alvimopan has proven to successfully decrease the duration of post-operative ileus and is FDA approved for such use in patients who have undergone bowel resection. Ultimately, decreasing the interlude between operation and return of bowel function results in shorter hospital stays, lower hospital costs, and faster rehabilitation. We propose to study the effectiveness of Alvimopan in decreasing postoperative ileus time in patients undergoing ventral hernia repair, a cohort that we feel may benefit from the use of Alvimopan but that to date has not been studied.

2 STUDY HYPOTHESIS

In patients undergoing open ventral hernia repair, we hypothesize that Alvimopan (Entereg) is associated with accelerated gastrointestinal recovery and reduced length of hospital stay compared to placebo controls.

2.1 PRELIMINARY DATA

Fitzgibbons et al, (Creighton University) employed a single-center, randomized, double-blind trial, of Alvimopan in open and laparoscopic ventral hernia repair patients. Comparisons were made between the length of time (in post-operative days) until patient flatus, bowel movement, and discharge from hospital. The treatment group (Alvimopan) showed a trend toward first flatus, bowel movement, and hospital discharge compared to the placebo group. However, this was not significant due to the small sample number within the sample population. The study results reported by Fitzgibbon et al. warrant a larger sample size to determine the outcomes achieved with Alvimopan in ventral hernia patients.

3 STUDY OBJECTIVES AND ENDPOINTS

3.1 STUDY OBJECTIVES

3.1.1 PRIMARY OBJECTIVES:

Primary Objective: To investigate the efficacy and safety of Almimopan, 12mg, administered orally 30 to 90 minutes preoperatively and twice daily postoperatively for a maximum of 7 days (15 total doses) in conjunction with a standardization postoperative care pathway for managing postoperative ileus after ventral hernia repair.

3.1.2 SECONDARY OBJECTIVES:

Secondary Objective: To investigate the post-operative gastrointestinal recovery, and treatment related morbidity after ventral hernia repair.

3.2 STUDY ENDPOINTS

3.2.1 PRIMARY ENDPOINT:

[Length of time \(hrs/days\) to gastrointestinal tract recovery](#)

3.2.1.1 PRIMARY ENDPOINT DEFINITION:

Time to gastrointestinal recovery will be measured by the following: Time to first flatus, time to toleration of a liquid diet, time to toleration of a solid diet, time to toleration or oral pain medications, time to first bowel movement, time to GI-2 recovery, time to GI-3 recovery, incidence of nasogastric tube insertion, episodes of emesis, use of anti-nausea medication, nausea, bloating, incidence of diet reduction or restriction, and initiation of TPN.

Time to first flatus and time to first bowel movement are patient reported endpoints that occur during the hospitalization. Patients will be asked about flatus twice daily by the physician or a qualified study or clinical staff member. Additionally, patients will be instructed to notify the nurse following first flatus and/or bowel movement so that the time can be recorded.

Toleration of a diet and toleration of oral pain medication are defined as ingestion of diet or medications that occurs without vomiting or significant nausea for four hours following ingestion.

GI-2 recovery is defined as both toleration of solid food and occurrence of first bowel movement. GI-3 recovery is defined as toleration of solid food and either occurrence of first flatus or occurrence of first bowel movement.

Patients requiring nasogastric tube insertion, requiring reduction or restriction of diet, having episodes of emesis, and/or needing initiation of TPN will be recorded. VAS

nausea, bloating and pain scores will be recorded by nursing staff at least twice each day. The number of doses of anti-nausea medication administered during the hospitalization will also be recorded.

3.2.2 *SECONDARY ENDPOINT(S):*

[Length of hospital stay](#), 30-day treatment related morbidity and re-admission rates, and post-operative pain scores.

3.2.2.1 *SECONDARY ENDPOINT DEFINITION(S):*

Length of stay will be measured in hours from the time that surgery is completed until the hospital discharge order is written (hrs/days).

Treatment related morbidity and re-admission rates will be assessed from the time surgery is completed to 30-days post-operatively. Treatment related morbidity and re-admission rates include: POI, indigestion, and any event determined by the attending physician to be directly related to treatment.

Post-operative pain scores will be obtained from patients daily until hospital discharge, 2-weeks post-operatively, and 30-days post-operatively using the Visual Analog Pain Scale (scale, 1-10) and the Hernia-Related Quality-of-Life Survey (HerQLes).

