4.3.3 SAMPLE SIZE DETERMINATION

A total of 140 patients are expected to undergo research related treatments. The study will contain one open surgery arm. The open surgery arm will be a single-site prospective, randomized, double-blinded, placebo-controlled clinical trial with 1:1

randomization between the study drug and placebo with 70 patients in each group for a total of 140 patients in the study. An interim evaluation of efficacy will be conducted separately in the open surgery arm when half the patients have been recruited.

This study is expected to enroll up to 140 subjects from one academic medical center (Froedtert Hospital and the Medical College of Wisconsin) a site that performs state of the art hernia repairs and is a high volume hernia practices.

The study has been designed to provide at least 80% power to detect a 24-hour decrease in the time to return of bowel function in the treatment group compared to the control group at a one-sided 2.5% significance level. This corresponds to a two-sided 5% significance level, but acknowledges the one-sided nature of the study hypothesis. Based on data from studies of the experimental treatment in other contexts, as well as internal data, we expect a standard deviation of 48 hours. Adjusting for the increase in sample size to accommodate the planned interim analysis, 64 evaluable patients per group will provide the desired power. More details of the power characteristics are shown under the Interim Analysis section. We will recruit 70 patients in each arm to accommodate a 5-10% dropout rate.

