5.3 PROCEDURES

Patients who meet all inclusion criteria will undergo the study related procedures stated below.

During enrollment, FH IDS will assign medication to patients in order of enrollment and according to the randomization code list. The patient will then receive medication dispensed from the bottle with the corresponding study ID.

Patient treatment will follow (section 5.1).

Following surgery, patients will be admitted to the hospital and a basic standardized treatment pathway will be initiated.

- 1) Following surgery patients are admitted with NPO status, PRN IV opioid pain medication, and PRN IV anti-nausea medication.
- 2) Epidural use is up to the discretions of the treating surgeon.
 - a. Non-narcotic adjuncts can be used as determined by the physician

- 3) Nasogastric tubes are NOT routinely left in following surgery. However, nasogastric tube use is up to the discretion of the treating surgeon. Patients who require NGT will be excluded from the study.
- 4) Patients remain NPO until the following criteria are met: reported flatus, absence of nausea and/or emesis and/or bloating, and absence of abdominal distention. Alternatively, clinical determination made by the physician can be utilized for diet advancement. If clinical determination outside of these parameters is used then the justification for the clinical decision making will be recorded for these patients.
- 5) Transition to oral pain medication will occur at or after the time of transition to clear liquids.
- 6) Diet advancement after clears will occur at physician discretion
- 7) Minimum discharge criteria include: toleration of diet beyond clears, toleration of oral pain medication, and absence of nausea/vomiting/distention.
 - a. Toleration of solid food is NOT required for discharge
 - b. Production of a bowel movement is NOT required for discharge

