6 DATA COLLECTION AND ANALYSIS

6.1 DATA COLLECTION

For each subject who meets inclusion criteria, a clinical report form (CRF) must be completed and signed by the investigator to certify that the data within each CRF are complete and correct according to data collection schedule (Appendix I). Every effort

should be made to respond to all questions on each CRF page, completion of the data is required by the protocol. The header section of each CRF page should be completed to identify the Investigators/surgeon and subject identification.

Upon receipt of completed CRFs and prior to entering data into the aggregate data summary table, the site-coordinator will ensure the accuracy of data recorded by comparison to supporting source documents. Adherence to proper recording of information as well as assuring that corrections are being made will also be addressed.

One interim analysis will be conducted when the first half of patients in each group (35 treatment and 35 control) complete their 30-day follow-up visit. Specifically, the interim analysis will be blinded and conducted at a nominal 0.0031 one-sided level of significance, while the final analysis will be conducted at a nominal 0.0219 one-sided level of significance. These values were calculated using a third-degree Kim-DeMets power alpha-spending function evaluated at the halfway point. If the actual information fraction at the time of the analysis is different, or the DSMC requests additional unblinded analysis, the significance levels will be adjusted using the alpha-spending function.

Results of the interim analysis will determine if it is futile to continue patient enrollment based on statistically significant differences (24 hour decrease in the time to return of bowel function in the treatment group compared to controls at a one-sided 2.5% significance level between the treatment and control groups). In addition, the MCW IRB in collaboration with the study investigators may terminate the study at any time to maintain patient safety.

The following table shows the probability of early stopping and the overall power of the study for various hypothetical effect sizes. If the design assumptions are correct, the study will stop early for efficacy with 23% probability, but if the actual effect is 50% larger (due to larger mean difference or smaller within-group standard deviation), then the trial will stop early 60% of the time.

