6.3 DATA / STATISTICAL ANALYSIS

All efficacy analyses will be intent to treat. The time to bowel function recovery and hospital length of stay will be compared between the two groups using Student's t-test. Due to the short-term nature of the outcome measures we expect no censoring.

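### The primary endpoint lists seven candidate times without choosing one, so the bowel-function time that carries the power, interim boundary and t-test is unidentified

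*Combined protocol and SAP*

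**What the plan says.** Section 3.2.1 names one primary endpoint, time to gastrointestinal tract recovery. Section 3.2.1.1 then defines it: "Time to gastrointestinal recovery will be measured by the following: Time to first flatus, time to toleration of a liquid diet", followed by twelve more items. Seven of the 14 are times: flatus, liquid diet, solid diet, oral pain medication, bowel movement, GI-2 and GI-3. The other seven are incidences, counts or scores (nasogastric tube, emesis, anti-nausea medication, nausea, bloating, diet restriction, TPN). GI-2 and GI-3 are defined, but neither is designated primary.

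The quantitative parts of the plan use other terms:

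- Section 4.3.3 bases 80% power on a "24-hour decrease in the time to return of bowel function in the treatment group", with a 48 h standard deviation.
- Section 6.1 ties the interim to a "24 hour decrease in the time to return of bowel function in the treatment group compared to controls", with nominal one-sided levels of 0.0031 and 0.0219.
- Section 6.3 states: "The time to bowel function recovery and hospital length of stay will be compared between the two groups", by t-test, and adds: "Due to the short-term nature of the outcome measures we expect no censoring".

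Length of stay has a clock: "Length of stay will be measured in hours from the time that surgery is completed until the hospital discharge order is written". No start is stated for any of the seven recovery times.

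On observability, section 3.2.1.1 treats flatus and bowel movement as events of the hospital stay. Section 5.3 item 7 requires neither solid food nor a bowel movement for discharge.

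**The concern.** A one-sided 2.5% level protects one variable fixed in advance. The plan describes one test, but the variable has a label that matches no listed item. Following the text as written, an analyst could let any of several times carry the primary claim once results are known, and 2.5% would then no longer be the error rate.

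Two further things depend on the missing name. The 24 h difference, the 48 h SD and the interim boundary cannot be checked against, or applied to, a variable that has not been identified. And whether a t-test without censoring is tenable differs between the candidates.

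**Working it through.** **1. Which items could be the tested variable.** A difference in hours, an SD in hours and a t-test of a time can apply only to a time. That removes seven of the 14 items and leaves seven. Where flatus precedes diet, as in section 5.3 item 4 ("Patients remain NPO until the following criteria are met: reported flatus"), GI-3 (solid food plus flatus or bowel movement) equals time to solid diet, so six distinct variables remain on that path.

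**2. The plan's own power, for one variable.** Inputs from sections 4.3.3 and 6.1: difference 24 h, SD 48 h, 64 per group, one-sided 0.025, cubic spending at half information.

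- Interim spend: 0.025 × 0.5³ = 0.003125, so z₁ = 2.734. The final boundary that uses up 0.025 is z₂ = 1.983, a nominal level of about 0.0237.
- Expected final z: 24 / (48 × √(2/64)) = 2.828. Expected interim z: 2.828 × √0.5 = 2.000.
- Interim power: Φ(2.000 − 2.734) = 23.1%. The final look adds 57.2%, for a total of 80.4% (80.35% before rounding). The plan's table gives 22.9% + 57.1% = 80.0%.
- With the final level that section 6.1 states, 0.0219, overall power is 79.4% and the overall one-sided error for one variable is 2.32%.

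The sample size therefore reproduces for one variable, with a small shortfall at the stated 0.0219.

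**3. What the unidentified SD means for power.** Fixed design, 64 per group, 24 h held, SD assumed: power = Φ(24 / (SD × √(2/64)) − 1.96).

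| Assumed SD | 36 h | 48 h | 60 h | 72 h |
|---|---|---|---|---|
| Power | 96.5% | 80.7% | 61.9% | 47.0% |

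**4. Error if the time is chosen after the data are seen.** Simulation with no treatment effect, 64 per arm and 100,000 trials per setting (Monte Carlo SE at most 0.0011), counting trials in which any of the seven one-sided t-tests rejects. The event chain follows section 5.3, but the distributions and gaps are assumptions. Flatus is gamma with mean 60 h and SD 48 h. Liquid diet is flatus + 4 h + an exponential gap a. Solid diet is liquid + b, oral medication is liquid + c, and bowel movement is flatus + d. GI-2 and GI-3 are derived from these. The two-look column uses 0.0031 at 32 per arm and 0.0219 at 64.

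| Mean gaps a/b/c/d (h) | Single look at 2.5% | Two looks |
|---|---|---|
| 6/12/6/12 | 3.9% | 3.6% |
| 12/24/12/24 | 5.3% | 5.0% |
| 12/24/12/48 | 6.0% | 5.7% |
| 24/48/24/48 | 7.5% | 7.1% |
| 12/24/12/24, 20% advanced independently of flatus | 6.6% | 6.2% |
| 12/24/12/24, 40% advanced independently of flatus | 7.2% | 6.8% |

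The reference value is 2.5% for the single look and 2.32% for two looks. Each test alone stays at 2.4% to 2.6%. If the choice is only between flatus and bowel movement, the single-look figure is 3.0% to 4.9%; the top is the independent case, 1 − 0.975² = 4.9%. If the five base times were independent, with GI-2 and GI-3 derived from them, it would be 14.0%, which the pathway makes unlikely.

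**5. Which candidates can be unobserved at discharge (section 5.3).**

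| Candidate | Needed before discharge? | Can be unobserved? |
|---|---|---|
| Liquid diet, oral pain medication | Yes, by item 7 | Not on the pathway |
| Flatus | Normally, through item 4 | Less often: physician-determined diet advancement, or non-report |
| Solid diet, bowel movement, GI-2, GI-3 | No | Yes |

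The expectation of no censoring in section 6.3 can therefore hold for some candidates and not for others.

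**The case against.** The best defence is that the plan narrows itself. Only a time can be tested, and section 6.3 describes a single comparison for this construct. Bowel function most naturally means flatus or bowel movement, the two recovery measures compared in the preliminary study in section 2.1. The candidate times are also strongly related. Much of this stands, and it is why the smaller 3% to 5% range is given alongside the wider one. But the natural reading is an inference. The plan does not state it, it still leaves two variables, and section 2.1 reports those two separately.

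A reader might infer more than the documents support:

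- That all 14 items, or all seven times, will each be tested at 2.5%. The plan does not say this.
- That the sample size is wrong. For one variable it is not, apart from the small difference at 0.0219.
- That the objectives contradict the endpoint, because section 3.1.2 reads "Secondary Objective: To investigate the post-operative gastrointestinal recovery, and treatment related morbidity after ventral hernia repair". The primary objective concerns efficacy in managing postoperative ileus. Overlapping wording is untidy but not a contradiction.
- That the t-test must be replaced. That depends on which time is named.

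The data collection schedule (Appendix I) is not in the text supplied, so the missing link is established only for that text.

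**Conclusion.** The point holds and should be settled before any unblinded comparison. It is a gap in the text and does not depend on the simulation: one primary endpoint, seven candidate times, and a differently worded tested variable tied to none of them and without a time origin.

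The error figures apply only if the variable is chosen after the data are seen. They are about 3% to 5% for flatus versus bowel movement and about 4% to 8% across the listed times at a single look. Under the plan's two looks the wider range is 3.6% to 7.1%, against 2.3% for one variable. They rest on an assumed flatus distribution and assumed gaps, none of which the documents supply.

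Power for the eventual primary measure is unknown until it is confirmed that the 24 h and 48 h figures belong to it. The in-hospital wording of section 3.2.1.1 and the no-censoring statement in section 6.3 need reconciling with section 5.3 item 7 if the named time is solid diet, bowel movement, GI-2 or GI-3.

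**What to change.** Before any unblinded comparison:

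1. Name one already-defined time as the sole primary endpoint in section 3.2.1 and state its time origin, for example end of surgery, as already used for length of stay.
2. Use exactly that name in sections 4.3.3, 6.1 (including the interim boundary) and 6.3.
3. Make the other 13 items secondary or supportive.
4. Confirm that the 24 h difference and 48 h SD apply to the named measure, or restate the power.
5. If the named measure can be unobserved at discharge, drop the no-censoring statement and pre-specify how unobserved events are analysed, for example by a time-to-event or rank-based method, with power restated to match. Otherwise the t-test can stay.

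Steps 1 to 3 are wording and need no new data. Step 5, if it applies, costs more: the mean-difference sample size and the half-information interim do not carry over automatically to a time-to-event test, and the required number may rise. The downside is that the other measures can no longer carry the primary claim, and the stated power may become less favourable.

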6.2 DATA VALIDATION

Data validation (verification of case report forms against source data documents) is required for both prospective and retrospective studies in which data is being entered on case report forms. Validation should be completed by an independent, study monitor, internal or external to the investigator/sponsor institution, who is not involved in the conduct or oversight of the study. For database studies you will be required to attest that you have entered into a data use agreement with the database owner and that the data in the database has undergone validation/verification by that owner. A technical guide is available upon request to assist you in completing the following section.

The study team's certified clinical research professional (CCRP) will review all data fields on the data collections forms. Data validation will occur after patients complete their final assessment at 30-days. Charts will be reviewed in batches of five. A list of missing data or data fields that need to be updated will be created. All errors, if any, will be identified and corrected. When all variables are reviewed, the CCRP will review the action items with the study team. Corrected fields on the paper data collection form will be dated and initialed by the study team.

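### First bowel movement is timed only if the patient volunteers it: section 3.2.1.1 schedules a staff question for flatus alone, and no described check could recover an uncharted time

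*Combined protocol and SAP*

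**What the plan says.** Section 3.2.1.1 treats the two bowel events as the same kind of data: "Time to first flatus and time to first bowel movement are patient reported endpoints that occur during the hospitalization". It gives two capture routes. The first is a scheduled question, for flatus only: "Patients will be asked about flatus twice daily by the physician or a qualified study or clinical staff member". The second depends on the patient and covers both events: "patients will be instructed to notify the nurse following first flatus and/or bowel movement so that the time can be recorded".

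Bowel-movement time is one of the measures listed under the primary endpoint. It also enters a composite: "GI-2 recovery is defined as both toleration of solid food and occurrence of first bowel movement". GI-3 is looser and can be met with solid food plus flatus.

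Section 5.3 (item 7) lets a patient go home without a bowel movement and without tolerating solid food. Section 6.3 compares recovery times by t-test, expects no censoring and gives no missing-data rule.

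Three data checks are described. Section 6.1 has the investigator certify each CRF as complete and correct, and has the site coordinator compare completed CRFs with source before data entry. Neither step is dated. Section 6.2 adds a later review: "Data validation will occur after patients complete their final assessment at 30-days. Charts will be reviewed in batches of five". At that review, "A list of missing data or data fields that need to be updated will be created".

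**The concern.** The time of a bowel movement can be observed properly only on the ward, close to the event. The plan leaves that observation to a postoperative patient remembering to mention it, while the less specific event, flatus, gets a routine question. The target difference is 24 hours (section 4.3.3), so recall weeks later is a poor substitute for a charted time.

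There are two stakes. One is precision: lost times reduce the number of patients contributing to bowel-movement time and GI-2. The other is interpretation. An event that happened but went unreported and an event that had not happened by discharge leave the same empty field. They need different handling: the first is a missing value, and the second is a patient known to be slow to recover.

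**Working it through.** **1. Capture routes for the two patient-reported events**

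| Event | Scheduled staff question | Patient tells nurse | Other point of care that needs it |
|---|---|---|---|
| First flatus | Twice daily (3.2.1.1) | Yes (3.2.1.1) | One of the criteria for starting diet (5.3, item 4) |
| First bowel movement | None in the text available | Yes (3.2.1.1) | None; not needed for discharge (5.3, item 7b) |

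If the answers are charted, a flatus time the patient did not volunteer is still bounded to about half a day. An unreported bowel movement has no such bound.

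**2. What the described checks can recover**

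- *Reported and charted:* the time stays in the source record and can be retrieved by any check, including one after day 30.
- *Occurred, neither reported nor charted:* nothing is in source. The section 6.1 certification can show the field is empty, but neither it nor the comparison with source can fill it. The section 6.2 review can only list it.
- *Not occurred by discharge:* nothing is in source here either. The field looks the same as in the previous case.

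A check before discharge, while the patient can still be asked, would separate the last two cases. None is described.

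**3. Timing of the section 6.2 review**

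Section 8 expects 40 patients a year, so 365 / 40 = 9.1 days between patients. Assume even accrual and that each batch waits for five consecutive patients; the plan states neither. The first chart of a batch is then reviewed about 30 + 4 × 9.1 = 66 days after surgery, and the last about 30 days after. The exact lag matters little, because an uncharted hour is unreliable at either point.

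**4. The plan's sample size, reproduced**

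Inputs from section 4.3.3: difference 24 h, SD 48 h, one-sided 2.5%, power 80%. Fixed design:

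n = 2 × (1.96 + 0.84)² × 48² / 24² ≈ 62.8, so 63 per arm.

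With one interim look at half the information and cubic alpha spending (0.025 × 0.5³ = 0.003125 at the interim), 63.4 per arm are needed, so 64 as stated. At 64 the probability of stopping at the interim is 23.1% and overall power is 80.4%; section 6.1 gives 22.9% and 80.0%. The plan's figures reproduce.

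**5. Illustrative effect of lost times**

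The documents give no loss rate, so the rates below are assumptions. They also assume that the analysed outcome needs bowel-movement time and that lost patients simply drop out of the comparison.

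| Assumed loss | n per arm from 64 | Power | n per arm from 70 | Power |
|---|---|---|---|---|
| 5% | 60.8 | 78.3% | 66.5 | 81.8% |
| 10% | 57.6 | 76.1% | 63.0 | 79.7% |
| 20% | 51.2 | 71.1% | 56.0 | 74.9% |
| 30% | 44.8 | 65.3% | 49.0 | 69.2% |

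The columns from 64 treat the dropout allowance as already used. The columns from 70 assume no other dropout. The margin is 70 − 64 = 6 per arm, or 6 / 70 = 8.6%, and section 4.3.3 already assigns it to a 5–10% dropout rate.

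**The case against.** The strongest reply is that capture is not absent. Patients are told to notify the nurse of either event, and ordinary nursing charting may record many bowel movements. That stands: the gap is one missing prompt for one item.

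Several stronger readings are tempting, and the documents do not support them.

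- *That nobody looks for missing fields until after day 30.* Section 6.1 separately requires the investigator to certify completeness. That step is undated, and nothing places it after day 30. It still cannot recreate an unrecorded time.
- *That patient-reported recovery times in general are at risk.* Flatus has two capture routes and is also a criterion for starting diet.
- *That a lost bowel-movement time is a lost primary outcome.* It removes bowel-movement time and GI-2. GI-3 may still be met through flatus, and sections 4.3.3 and 6.3 do not name which measure is tested.
- *That blanks will be filled by guesswork.* Section 6.2 speaks of listing and correcting fields, not of guessing.
- *That the plan as a whole never prompts for bowel movement.* Section 6.1 refers to a data collection schedule in Appendix I, which was not available for review and might contain a daily item.

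It is also fair that a pre-discharge check will meet legitimately empty fields, because section 5.3 allows discharge before a bowel movement or solid food. The remedy therefore has to provide a code for that state.

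**Conclusion.** The point holds as a gap in the capture method. In the available text, first bowel movement has no scheduled staff question, although it is a listed primary-endpoint measure and a required part of GI-2. A bowel movement neither reported nor charted in hospital cannot be reliably timed by any check described, and its empty field cannot be told from one that had not occurred by discharge.

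The size is unknown. The power figures, 78.3% down to 65.3% for an assumed 5% to 30% loss from 64 per arm, show sensitivity and are not estimates. With all 70 per arm otherwise retained, a 10% loss leaves 79.7%. The 66-day lag rests on even accrual and batches that wait to fill. The conclusion is limited to the text available, without Appendix I. This is a cheap improvement to make; it does not show that the trial's primary result would be lost.

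**What to change.** - **Section 3.2.1.1:** at each existing twice-daily contact, ask about both flatus and bowel movement, and record the clock time of each first event. Align Appendix I if it does not already carry the item.
- **Section 6.2:** add a brief check by existing study staff before discharge that each recovery time is either recorded or marked as not occurred by discharge. Keep the day-30 batch review for the remaining fields.

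The cost is one extra question per contact and a few minutes of form checking per patient. Discharge and diet rules are untouched. The check will not time bowel movements that happen after discharge, but it will show how many patients are in that position. That count is needed to judge whether the section 6.3 expectation of no censoring is tenable.
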